1.1.3 Hypothesis

Patients using MDC-T will reach individualized fasting plasma glucose (FPG) and HbA1c targets and MDC-M will help patients to maintain glycemic targets at 6 months from baseline.

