For those patients who do not reach target at 3 months, the DCES/HCP will partner with the patient (and physician provider, as needed) to assess the patient's ability and interest in continued use of the MDC-T app and determine the best course of action (either return to usual care or continued participation in the study). If deemed eligible, the patient will continue to have access to the MDC-T app with continued guidance from their respective HCP, in regards to insulin therapy recommendations. They will be asked to complete follow-up surveys at months 3 and 6, as well as permit access to pertinent medical record information (e.g., HbA1c values) for the duration of the study. Patients who stay in the study and continue to use the MDC-T app will receive another three-month supply of insulin pens (Lantus (U100) Solostar Pen or Toujeo (U300) Solostar Pen, as per treating Physician).

Phase 2 (Maintenance)

Patients who are successful in reaching their glycemic target and agree to continue participation, will be transitioned into Phase 2 of the study at their three-month clinic visit. At this time, the HCP (endocrinology provider and/or DCES) will introduce and train patients how to use the MDC-M app to support glycemic control. Patients will receive another three-month supply of insulin pens (Lantus (U100) Solostar Pen or Toujeo (U300) Solostar Pen (as per treating Physician) and asked to return for the final follow-up visit at six months (routine clinic visit). They also will be asked to complete follow-up surveys at months 3 and 6 to assess changes in behavioral and psychosocial factors that influence diabetes self-management as well as their acceptability and satisfaction with their experience using the MDC app. When possible, surveys will be completed at clinic visits. However, surveys may also be made available electronically or via mail should visits occur remotely (e.g., via telemedicine) or a patient cannot complete at a face-to-face visit (e.g., time constraints).

The DCES and endocrinology provider will be available throughout the course of the study to respond to any question or concerns that the patient may have regarding insulin titration, insulin dosing, and the MDC app specifically.

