2.4.1 Clinical Data/EMR Abstraction

Intervention Group

Phase1 (Titration) Clinical: HbA1c will serve as the primary outcome and clinical measure to determine the impact of the MDC-T app on glycemic control from baseline to 3 months. Related measures to be collected will include: Change in FBG from baseline to 3 months, rate of patients who attained individualized titration target, the time it took to attain titration target and number and type of hypoglycemic events, which are defined as follows:

- Mild/asymptomatic hypoglycemia blood glucose <70 mg/dl and no symptoms;
- Moderate/symptomatic hypoglycemia blood glucose <70 mg/dl and symptoms;
- Severe/symptomatic hypoglycemia requires assistance of another person to resuscitate because blood glucoses are too low to maintain consciousness.

Hypoglycemic data will be collected in the following ways:

1) ask the patient to contact study team if/when it happens,

- 2) ask patient at each study visit,
- 3) review of MDC information,
- 4) review of EMR,

Data will be collected on an AE form for each patient and reported if an SAE. In addition, blood pressure, cholesterol and BMI data will be retrieved from the patient's EMR record.

Phase 2 (Maintenance) Clinical: HbA1c will serve as the primary outcome to determine the longer term impact of MDC-M app on maintenance of glycemic control from 3 months to 6 months for those patients achieving glycemic targets during the MDC-T titration phase. Related measures to be collected will include the number of patients who maintained individualized glycemic targets, change in FBG from 3 months to 6 months, and record of reported hypoglycemic events (following same definitions and data collection plan as described for Phase 1). Additionally, blood pressure, cholesterol and BMI data will be retrieved from the patient's EMR record.

All of the aforementioned data will be collected for the intervention group in accordance with the study calendar in section 2.2.5.

Control Group

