2.5.2.2 Phase 2 (Maintenance)

- Proportion of patients maintaining their individualized HbA1c goal at 6 months as compared to the number of patients at target HbA1c at start of maintenance phase (month 3)
- Proportion of patients maintaining HbA1c <7% at 6 months compared to number of patients at target HbA1c <7% at start of maintenance phase (month 3)
- Change in HbA1c from baseline and 3 months to 6 months
- Change in FPG from baseline and 3 months to 6 months, if available
- Adherence to HCP recommended treatment plan
- Patient-reported changes in behavioral and psychosocial outcomes from baseline or 3 months to follow up time points (survey)
- Safety end points (including hypoglycemia, AEs)

• Number and type of technical complaints

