8.2 Obligations and Responsibilities of the External Sponsor

The External Sponsor shall be responsible for transmitting to Sanofi all AE's occurring with the use of Sanofi medicinal products.

All complaints and adverse events will be managed and reported in compliance with all applicable regulations and included in the final clinical study report.

For the intervention group:

- All AEs, regardless of seriousness or relationship to Sanofi Medicinal product and study medical devices (e.g., MDC app), spanning from the signature of the informed consent form until the end of the study as defined by the protocol for that patient, are to be recorded on the corresponding page(s) or screen(s) of the CRF.
- Any defect in the device or medical device complaint, with AE must be reported within 24 hours in case of potential Adverse Event or Serious Adverse Event or without AEs must be reported within 5 days by the Investigator in order for a product technical complaint to be completed. Appropriate information (e.g., samples, labels, or documents such as pictures or photocopies) related to product identification and product deficiencies may need to be gathered. The investigator will assess whether or not the quality issue has to be reported together with an AE or SAE.
- Whenever possible, diagnosis or single syndrome should be reported instead of symptoms. The Investigator should specify the date of onset, intensity, action taken with respect to Sanofi Medicinal product or Medical Device, corrective treatment/therapy given, additional investigations performed, outcome, and his/her opinion as to whether there is a reasonable possibility that the AE was caused by Sanofi Medicinal product(s), Medical Device or by the study procedure(s).
- The Investigator should take appropriate measures to follow all AEs until clinical recovery is complete and laboratory results have returned to normal, or until progression has been stabilized, or until death, in order to ensure the safety of the patients. This may imply that observations will continue beyond the last planned visit per protocol, and that

additional investigations may be requested by the monitoring team up to as noticed by the Sponsor.

- When treatment is prematurely discontinued, the patient's observations will continue until the end of the study as defined by the protocol for that patient.
- Laboratory, vital signs abnormalities are to be recorded as AEs only if:
 - Symptomatic and/or

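### Section 2.2.3 does not secure month-6 data for patients who miss target at month 3, so the baseline-to-6-month HbA1c change has no defined population and may depend on the month-3 result

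*Combined protocol and SAP*

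**What the plan says.** Section 2.2.3 splits the intervention group at the month-3 visit.

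- **At target:** "Patients who are successful in reaching their glycemic target and agree to continue participation, will be transitioned into Phase 2". Nothing is said about patients at target who do not agree.
- **Not at target:** the educator or other professional works with the patient to "assess the patient's ability and interest in continued use of the MDC-T app" and to "determine the best course of action (either return to usual care or continued participation in the study". Those judged eligible keep the titration app, complete the month-6 survey, and "permit access to pertinent medical record information (e.g., HbA1c values) for the duration of the study". No month-6 collection is described for those who go back to usual care.

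Section 2.4.1 limits the Phase 2 HbA1c outcome to "maintenance of glycemic control from 3 months to 6 months for those patients achieving glycemic targets during the MDC-T titration phase". Section 2.5.2.2 then lists "Change in HbA1c from baseline and 3 months to 6 months" without naming a population. It also lists FPG change and safety endpoints, and maintenance proportions that take patients at target at month 3 as the reference. Section 1.1.3 states the hypothesis that "MDC-M will help patients to maintain glycemic targets at 6 months from baseline".

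Three other places bear on follow-up. Section 8.2 says: "When treatment is prematurely discontinued, the patient's observations will continue until the end of the study as defined by the protocol for that patient". The study calendar (2.2.4 and 2.2.5) schedules 6-month laboratory, hypoglycemia and adverse-event data, but its 6-month column falls under the Phase 2 heading. Section 10 ends data collection when a participant chooses to withdraw, and its grounds for removal by investigators do not include missing target. Section 2.6.2 gives no 6-month analysis population and no rule for missing month-6 values.

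**The concern.** Whether a patient has a month-6 value may turn on the month-3 result together with a judgement of ability and interest for which no criterion is given. Patients who did poorly on titration, or coped poorly with the app, are the ones who can go unobserved. If so, the month-6 change from baseline describes responders plus a selected part of the non-responders, and the month-6 hypoglycemia and adverse-event counts have the same gap. A reader would naturally take an unqualified 6-month change from baseline as the result for patients given the app.

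The maintenance proportions have a smaller gap. Their reference group is everyone at target at month 3, but the plan does not say whether a patient at target who declines Phase 2 is followed, or how that patient is counted.

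**Working it through.** **The plan's own figures (section 2.6.1).** With 109 per arm, SD 1.5 and a two-sided 95% interval, the half-width is 1.96 × 1.5 × √(2/109) = 0.398, against the stated 0.40. The Phase 2 number is 0.70 × 109 = 76.3, stated as 76. Both reproduce. That leaves 109 − 76 = 33 patients not entering Phase 2.

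**Assumptions, because the documents give no figures.** All 33 are non-responders. Reaching target is treated as a cut on the month-3 HbA1c fall, which is normal with SD 1.5. The month-6 fall from baseline has the same SD and correlates with the month-3 fall at ρ = 0.5, 0.7 or 0.9. The share of non-responders followed to month 6 is varied.

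**Selection at month 3.** The responder share is p = 76/109 = 0.697, for which z = 0.517 and the normal density is 0.3491.

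- Responders' mean fall relative to all 109: 1.5 × 0.3491/0.697 = +0.75.
- Non-responders' mean fall relative to all 109: −1.5 × 0.3491/0.303 = −1.73.

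**Effect on the baseline-to-6-month change.** If a fraction f of the 33 is followed, the observed set exceeds the full group at month 3 by M = (76 × 0.751 − 33f × 1.730)/(76 + 33f). The month-6 overstatement is ρ × M.

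| Non-responders followed | n at month 6 | Responder share | M | Overstatement at ρ = 0.5 / 0.7 / 0.9 |
|---|---|---|---|---|
| All | 109 | 70% | 0 | 0 / 0 / 0 |
| Half | 92.5 | 82% | 0.31 | 0.15 / 0.22 / 0.28 |
| None | 76 | 100% | 0.75 | 0.38 / 0.53 / 0.68 |

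For scale, the 95% half-width of a single-arm mean change in all 109, carrying SD 1.5 to month 6, is 1.96 × 1.5/√109 = 0.28. The planned ±0.40 is a between-arm figure at month 3 and is not the right yardstick here.

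**Effect on the 3-to-6-month change.** The shift is (ρ − 1) × M. In responders alone it is −0.38, −0.23 and −0.08 at ρ = 0.5, 0.7 and 0.9. Regression to the mean makes HbA1c appear to worsen, so maintenance is understated.

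**Losing at-target decliners.** If 20% of the 76 were lost (60.8 left) and half of the 33 followed, M = (60.8 × 0.751 − 16.5 × 1.730)/77.3 = 0.22. The overstatement drops to 0.11, 0.16 and 0.20. If all 33 were followed, M = (60.8 × 0.751 − 33 × 1.730)/93.8 = −0.12, and the fall from baseline would be understated by 0.06 to 0.11.

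**The case against.** The strongest reply is that Phase 2 is meant to be about responders. Section 2.1, Aim 2 and section 2.4.1 all say so, and the 6-month HbA1c change sits under the Phase 2 heading. For that population the responders' mean is the correct answer. This stands for the maintenance outcome. It does not settle the change from baseline, because section 2.4.1 states its restriction for the 3-to-6-month outcome, the endpoint bullet in 2.5.2.2 names no population, and 2.2.3 keeps some non-target patients in the study with HbA1c access without saying whether they count.

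A second reply is that loss to month 6 is inferred. The calendar exempts no one, section 2.4.1 applies it to the intervention group, section 8.2 continues observation after early discontinuation, and missing target is not a ground for removal in section 10. This stands in part: loss is possible and not certain. But section 8.2 runs only to each patient's protocol-defined end of study, which is never defined for someone returned to usual care.

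A reader might also infer that at-target patients who decline Phase 2 leave the study and that this too inflates the result. The documents do not say they leave, and losing them would lower the responder share.

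Finally, Phase 2 is descriptive and has no 6-month comparison with usual care, so no between-group benefit at 6 months is at stake.

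**Conclusion.** The point holds as a gap in follow-up and in the definition of a secondary endpoint. Section 2.2.3 is not reconciled with section 8.2 or the calendar, and month-6 data can be missing according to the month-3 outcome. If the baseline-to-6-month change is read as applying to intervention patients generally, the fall could be overstated by anything from zero (all non-target patients followed) through about 0.15 to 0.3 (half followed) to about 0.4 to 0.7 point (none followed).

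Those figures depend on the assumptions stated. The 33 may include dropouts and at-target decliners, since section 2.6.1 does not split them. Individual targets will also separate patients less cleanly than a cut on HbA1c change, which would make the effect smaller.

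A reader might infer that the plan overstates the app's benefit in general. The documents do not support that. The primary endpoint is measured at month 3, before this routing can remove anyone; the responder-only maintenance outcome is the declared design; and the 3-to-6-month change in responders is biased in the unfavourable direction. This is a change worth making because it is cheap, and it does not threaten the main result.

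**What to change.** - In section 2.2.3, separate stopping the app from leaving the study, and reconcile that text with section 8.2 and the calendar by stating each patient's end of study for every month-3 route.
- Abstract routine record values of HbA1c and fasting glucose, plus hypoglycemia and adverse events, through month 6 for every intervention patient who has not withdrawn consent. This includes those returned to usual care and those at target who decline Phase 2.
- In sections 2.5.2.2 and 2.6.2, report the baseline-to-6-month change over all enrolled intervention patients alongside the Phase 2 subset, with counts by month-3 route and a stated rule for missing month-6 values.
- Keep the maintenance proportions among patients at target at month 3, with decliners in the denominator.

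The choice of care at month 3 stays with the treating professional and the patient.

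The cost is protocol wording, consent wording where needed, and abstraction for about 30 patients, with no added visits. The 6-month figure is likely to look less favourable. Hypoglycemia capture will be less complete in patients who stop the app, because section 2.4.1 also relies on patient contact, study visits and app data; the report should say so.

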2.2.4 Usual Care Group

A retrospective comparative group will be selected from eligible patients who previously were treated at the UPMC Diabetes Outpatient Clinics. This group was chosen for two reasons. First, patients seen at the UPMC Diabetes Specialty Outpatient Clinics have the most robust data available regarding insulin titration, including HbA1c and FBG and, for many patients, BG meter readings. Secondly, this particular group establishes a standard of specialty care against which to compare MDC and will uniquely inform the benefit of this digital tool. We postulate that if MDC produces outcomes, at the very least, equal to those of specialty practice, the likelihood of benefit to PC care is high. Patients in the usual care group will be identified using EMR data accessed through the UPMC Clinical Data Warehouse. As detailed in the Statistical Analysis Plan, propensity score matching will be used to pair intervention and usual care participants.

Study phase			Phase 2 (Maintenance)	
Visits	1	2	3	
Time point	Baseline	3 Months	6 Months	
Visit window		±2 weeks	±4 weeks	
Study Specific Procedures				
Informed Consent	Х			
Eligibility	Х			
MDC Installation and Education	Х	X ¹		
Patient Surveys ³	Х	Х	Х	
Health Care Provider Surveys ⁴	Х	Х	Х	
Reports of Technical Issues		Х	Х	

2.2.5 Study Calendar

Clinical Care/EMR Data Abstraction			
Demographics ⁵	Х		
Patient History ⁶	Х		
Vital signs ⁷	Х	Х	Х
Lab work ⁸	Х	Х	Х
Self-monitoring blood glucose (SMBG)		Х	Х
Provider visits (and Endocrinology escalation visits)		х	Х
Hypoglycemic events	Х	Х	Х
Hospital stays	Х	X	Х
Adverse events	Х	X	Х

1. Education on MDC-M app only for those participants who were able to reach target FBG/A1c transition to maintenance.

2. Diabetes Medication System Rating Questionnaire-Short Form (DMSRQ-SF), Diabetes Distress Scale (DDS17) at all time points; Usability and Satisfaction surveys as 3 and 6 months.

3. Health care provider perspectives and experiences on insulin dosing survey at baseline and usability and satisfaction survey at 3 months and completion of the study.

4. Participant name, age, gender, race, ethnicity, contact information, location, marital status, employment status, education level, health insurance information

5. Diabetes duration, diabetes-related medication, diabetes-related hospitalizations, hypoglycemic events within the past year, co-morbidities

6. Blood pressure, weight, BMI

7. Fasting blood glucose, HbA1c, cholesterol, lipids (if available in clinical records); baseline values may have been collected and recorded up to nine months prior to study start (e.g., lipid panels are usually conducted once a year).

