A majority of the data is also expected to be available within the EMR for the control group. HbA1c, FBG, blood pressure, cholesterol, and BMI data should be recorded and accessible for patients. In addition, many patients also have BG meter readings. At a minimum, we will select patients who have HbA1c values that correspond to baseline [index date = date of insulin initiation] and follow-up time points/time frames that correspond with those described in the study calendar (section 2.2.5). EMR records, including notes, downloads, and related documented data will be reviewed to identify and classify hypoglycemic events according to already aformentioned definitions.

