2.5 Study Endpoints

2.5.1 Primary Endpoint

Change in HbA1c at 3 months as compared to patients using standard of care.

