2.5.2 Secondary Endpoints

2.5.2.1 Phase 1 (Titration)

- Change in HbA1c from baseline to 3 months within and between groups
- Proportion of patients reaching HbA1c <7% at 3 months as compared to patients using SOC
- Change in FPG from baseline to 3 months within and between groups
- Patient-reported changes in behavioral and psychosocial outcomes from baseline to 3 months (survey)
- Patient-reported acceptability of and satisfaction with MDC-T (survey)
- Provider-reported acceptability of and satisfaction with MDC-T (survey)
- Rate of escalation to Endo (Endocrine visits) for patients using MDC-T
- Safety end points (including hypoglycemia, any untoward adverse events)
- Number and type of technical complaints

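### The study calendar's nine-month allowance for baseline labs covers HbA1c and fasting glucose as well as lipids, and nothing else limits the age of the baseline behind the 3-month HbA1c change

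*Combined protocol and SAP*

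**What the plan says.** The note to the laboratory row of the study calendar (section 2.2.5) gives one list, "Fasting blood glucose, HbA1c, cholesterol, lipids (if available in clinical records", and then one allowance for the whole list: "baseline values may have been collected and recorded up to nine months prior to study start". The illustration offered is that "lipid panels are usually conducted once a year".

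Section 2.4.1 makes HbA1c the Phase 1 primary outcome, used to "determine the impact of the MDC-T app on glycemic control from baseline to 3 months". It then adds: "All of the aforementioned data will be collected for the intervention group in accordance with the study calendar in section 2.2.5". The primary endpoint (2.5.1) is "Change in HbA1c at 3 months as compared to patients using standard of care". The first Phase 1 secondary endpoint (2.5.2.1) is "Change in HbA1c from baseline to 3 months within and between groups".

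For controls, section 2.4.1 asks for "HbA1c values that correspond to baseline [index date = date of insulin initiation". It refers to the same calendar for follow-up time frames and states no number of days or months around the index date.

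The calendar marks lab work at baseline, month 3 and month 6. Month 3 has a ±2 week visit window; the baseline window cell is blank. The HbA1c threshold of 7.5% in sections 3.1, 3.2.1 and 3.2.2 carries no date. Section 2.6.2 puts baseline HbA1c in the propensity score and names baseline fasting glucose as the fixed covariate in the mixed model.

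**The concern.** The reason given for the allowance suits lipids, which are measured about yearly. It does not suit HbA1c or fasting glucose, which are the outcome, the eligibility test, a matching variable and a model covariate. Read as written, an abstractor may take an HbA1c from well before the patient began using the app and call it baseline.

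Three uses are then exposed. The 7.5% criterion may be met by a value that no longer describes the patient. Matching may pair people on values of different ages. And the change score may include months before the intervention. The planned analysis does not repair this: the fasting glucose covariate has the same allowance, and nothing adjusts for the age of the baseline value. The comparison is not randomized, so nothing makes those ages alike in the two groups.

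**Working it through.** **Inputs.** Baseline age 0 to 9 months (2.2.5 note). Month-3 window ±2 weeks (study calendar). SD of 3-month HbA1c change 1.5, 109 per group, stated precision ±0.40 (2.6.1). 95% confidence interval (2.6.2).

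**Plan's own figure.** Half-width = 1.96 × SD × √(2/n) = 1.96 × 1.5 × √(2/109) = 0.398. This reproduces the stated ±0.40, so the sample size arithmetic is not in question.

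**Interval behind the 3-month change.** Two weeks is 14/30.4375 = 0.46 month. Interval = age of baseline value + 3 ± 0.46 months, taking the month-3 sample to fall in its visit window and *study start* to be the patient's baseline visit.

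| Age of baseline HbA1c | Shortest interval (months) | Longest interval (months) |
|---|---|---|
| 0 months | 2.54 | 3.46 |
| 9 months (limit in the note) | 11.54 | 12.46 |

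At the limit, 9/12.46 = 72% to 9/11.54 = 78% of the interval lies before the baseline visit. This is the extreme case; the documents do not say how often old values would occur.

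**Other reading of *study start*.** Section 3.2.2 counts three years back from *study start* and appears to mean the start of the trial. On that reading the age of a patient's baseline value also grows with enrolment time, and 12.5 months is not a ceiling.

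**Which estimates are affected.** Write the recorded baseline as the value at the index date plus a drift d that depends on its age.
- Within-group change is shifted by −mean(d). Nothing cancels it.
- The between-group difference in change is shifted by −[mean(d, intervention) − mean(d, control)]. If ages are equal, and drift at a given age is alike in the two groups, this is about zero.

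**Scale, as an assumption only.** A between-group drift difference of 0.1, 0.2 or 0.4 HbA1c points would be 25%, 50% or 100% of the 0.398 half-width. The documents do not say whether any of these is likely.

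**Cost of a window in pairs.** Half-width at 98 pairs (10% lost): 1.96 × 1.5 × √(2/98) = 0.420. At 87 pairs (20% lost): 1.96 × 1.5 × √(2/87) = 0.446. With a 3-month window the longest interval is 3 + 3.46 = 6.46 months.

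**The case against.** The best defence is that lipids were all that was meant. Baseline lab work is scheduled in the calendar like the later visits, eligibility is checked at baseline, and the note reads as a fallback for values already in the record. That may be the intent. But lipids appear only as an example, no sentence separates HbA1c from them, and abstractors work from the text. The calendar's superscripts and note numbers are one apart, but the content identifies this as the laboratory note.

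A second defence is that controls are anchored at insulin initiation. That is so, and the point is therefore firmest for the intervention group. The anchor still has no window.

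The third defence limits the harm, and it stands. The primary endpoint is a between-group comparison, and baseline HbA1c is in the propensity score. With equal baseline ages and good matching, the contrast is close to the month-3 difference between groups. A reader might infer that the primary result is biased merely because old values are allowed. The documents do not support that: bias needs unequal ages, and nothing shows they will be unequal.

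A reader might also infer that the two groups start from different clinical moments, because sections 1.2.1 and 3.2.1 speak of titration and section 5.1.1 of starting insulin. But section 2.2.3 describes these patients as new to insulin and section 2.3 describes starting a regimen, which points to the control anchor. Nor is the month-3 timing for controls left open: section 2.4.1 already ties it to the calendar.

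**Conclusion.** The point holds as a gap in the definition of baseline. A stated rule admits HbA1c and fasting glucose values up to nine months old, and no section sets a tighter numeric limit in either group. The interval behind the 3-month change is about 2.5 to 12.5 months if *study start* is the patient's baseline visit, and has no fixed per-patient maximum if it is the start of the trial.

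The within-group 3-month change, the eligibility check and the matching variable are directly exposed. For the primary contrast the risk is conditional: about zero if baseline ages are equal and drift is alike, and of unknown size and direction otherwise. It would go too far to say that the primary estimate is biased, or that 12.5 months is a firm maximum. The point should be fixed before baseline values are abstracted, because a timely baseline cannot be recovered afterwards.

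**What to change.** In section 2.2.5, confine the nine-month allowance to lipids and similar secondary labs. Replace *study start* in that note with a per-patient index date: the baseline and training visit for intervention patients, and insulin initiation for controls, as section 2.4.1 already has it. In sections 2.4.1 and 2.6.2, define baseline HbA1c and fasting glucose in both groups as the last value on or before the index date within one common window, for example 3 months. Apply the same window to the HbA1c criterion in sections 3.2.1 and 3.2.2. Fix its length after counting the available dates and before any outcome is seen.

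The cost is wording, one count of dates, and some patients or controls without a value in the window. They are lost or replaced. The documents set no cap of 109 on the pool from which controls are drawn, and intervention patients can be screened at enrolment. Section 6.1 rules out clinical procedures beyond usual care, so any new draw would have to be part of routine care. The share affected is not in the documents. If pairs are lost, precision falls as shown above. A shorter window gives a cleaner 3-month change but loses more people.

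Optional: a sensitivity analysis adjusted for the age of the baseline HbA1c, and aligned wording on insulin status in sections 1.2.1, 3.2.1 and 5.1.1.
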